	
crossover part of the study will be analyzed by means of proportional hazard time-depended analysis. Median disease-free survival will be calculated with the Kaplan-Meier method.
 
All statistical testing is two-sided at the nominal 5% significance level, with no adjustment for multiplicity. All patients who receive at least one regorafenib plus durvalumab dose will be included in the safety analysis.

Publication plan	
 - Timelines 2025 Q4 - Target Journals: Lancet, Lancet Oncology, JCO.

Table 1. SCREENING PHASE

	28 to 1 day before randomization ^d	
Informed consent	X	
Inclusion / Exclusion criteria	X	
General disease medical history	X	
Prior / Concomitant medications	X	
Complete physical examination	X	
ECOG PS	X	
Weight	X	
Vital Signs ^a	X	
12-lead ECG ^b	X	
Tumor imaging ^c	X	Must be performed within 10 weeks before D1C1. Tumor imaging can be accepted even if performed before the procedures to obtain NED status.
Hematology, chemistry, coagulation and pregnancy test ^d	X	
Biomarkers ^d	X	CEA and CA 19-9 must be on normal range
Histologic Confirmation	X	Only if surgery performed to obtain NED state, resection of the metastases must be R0

Table 2. Experimental arm

	From -7 days to Day 1 Cycle 1	Day 1 Cycle 1	Day 8, 15, 22 Cycle 1	Day 1 Cycle 2	Day 15 Cycle 2	Day 1 Cycle 3 and above up to 1-year (12 cycles)	QW12 from C1D1 (+/- 7 days)	End of treatment visit	Treatment discontinuation 30-days from last treatment or at initiation of other anticancer therapy (whichever occurs first)	Follow-up period ^g
Prior / Concomitant medications								X		X
Complete physical examination								X		X
Limited physical examination ^a		X	X	X	X	X				
ECOG PS		X	X	X	X	X		X		X
Weight		X		X		X				
Vital Signs ^a		X	X	X	X	X		X		X
12-lead ECG ^b								X		

Tumor imaging/ response assessments ^c							X	X		X
Hematology ^d	X		X	X	X	X		X		
Coagulation ^d	X							X		
Chemistry ^d	X		X	X	X	X		X		
Biomarkers ^d							X	X		X
Durvalumab Administration		X ^e		X ^e		X ^f				
Regorafenib Administration		X ^e		X ^e		X ^f				
AEs assessments	X		X	X	X	X		X	X	X
Survival and anti-cancer therapy									X	X

Table 3 - Control arm

	QW12 from C1D1 (+/- 7 days)	End of treatment visit	Treatment discontinuation 30-days from last treatment or at initiation of other anticancer therapy (whichever occurs first)	Follow-up period ^g
Prior / Concomitant medications	X	X		X
Complete physical examination	X	X		X
ECOG PS	X	X		X
Weight	X	X		
Vital Signs ^a	X	X		X

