- Hematology profile (CBC, including RBC count, hemoglobin, hematocrit, WBC count with differential [neutrophils, eosinophils, lymphocytes, monocytes, basophils] and platelet count)
- Coagulation profile (aPTT, PT, INR)
- Chemistry profile includes Na, K, Cl, Mg, Ca, P, blood urea nitrogen, creatinine, glucose, total protein, albumin, AST, ALT, alkaline phosphatase, total bilirubin, LDH, amylase, lipase
- Pregnancy test (a positive urine test will be confirmed with a serum pregnancy test) during the study (for woman of childbearing potential). If a patient becomes pregnant while in the study, the study treatment must be immediately discontinued. Pregnancy information for a female patient or for the female partner of a male patient should be reported within 24 hours from the time the Investigator first becomes aware of a pregnancy or its outcome.
- Biomarkers: CEA, Ca19.9, backup plasma sample.

Samples for hematology, serum chemistry, coagulation, pregnancy test and biomarkers will be analyzed at the study site's local laboratory. Investigator may have additional blood tests performed for the purpose of planning treatment administration, dose modification, or following AEs.

Procedure does not have to be repeated if performed within 72 hours prior to Cycle 1 Day 1 (i.e. first day of dosing)

- e) The first administration of Regorafenib + Durvalumab must be done within 10 weeks from NED state. Patients who are rendered NED and have received an adjuvant program are still eligible, provided they are randomized within 1 month since the last chemotherapy cycle
- f) Up to 1 year
- g) During the early follow up phase (Month 13-Month 24) all patients will undergo the following visit every 4 months. During the late follow up phase (Month 25 to Month 60) all patients will undergo the following visit every 6 months.

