8.1 Study Visits

8.1.1 Screening

Screening, to verify inclusion and exclusion criteria, will include:

1. obtaining written informed consent from patient or legally authorised representative (Section 8.2.1.1)
2. Review of eligibility criteria
3. documentation of demographics and medical history (Section 8.2.1.2)
4. Complete physical examination (Section 8.2.2.1)
5. vital signs (Section 8.2.2.2)
6. ECOG performance status (Section 8.2.2.3)
7. 12-lead electrocardiogram (ECG; Section 8.2.2.4)
8. clinical chemistry, coagulation profile and haematology (Section 8.2.2.45)
9. CEA and CA 19-9 analysis, backup plasma sample (Section 8.2.3.2)
10. pregnancy test (serum or urine) for female patients of child-bearing potential (Section 8.2.1.3); patients with positive results will be discontinued from the study with no further study procedures performed
11. CT/MRI/PET scan of chest and abdomen with tumor measurement and evaluation by RECIST 1.1 criteria (Section 8.2.3.3)
12. documentation of prior and concomitant medications (Section 7.7)
13. Histological confirmation

Patients who meet the inclusion/exclusion criteria (Section 6) will be randomized to one of the following:

1. Treatment arm (Regorafenib + Durvalumab)
2. Control arm

8.1.2 Treatment Phase: Table 2 and 3.

Patients allocated to regorafenib + durvalumab arm will undergo visits every week for the first cycle, every 2 weeks for the second cycle, and monthly thereafter.

Patients allocated to the control group will undergo visits every 12 weeks.

If at any time a relapse is confirmed, the patient will discontinue treatment. Patients in the control arm will be offered to crossover to regorafenib plus durvalumab.

All visits have a window of ± 7 days.

- Patients allocated to Treatment arms will undergo the following procedures and assessments:

At each visit:

1. Limited physical examination
 2. vital signs
 3. ECOG performance status
 4. Weight
 5. Clinical chemistry and haematology (CBC + differential platelet count; creatinine; total bilirubin; AST; ALT; alkaline phosphatase; LDH; albumin; glucose; potassium; sodium; calcium)
 6. administration of therapy (regorafenib plus durvalumab at Day 1 of every cycle)
 7. documentation of AEs/SAEs
 8. documentation of concomitant medications and procedures (at Day 1 of every cycle)
 9. CEA and CA19-9 analysis and CT/MRI/PET scan as per baseline assessment: every 12 weeks. From day 1 (\pm 7 days).

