- Patients allocated to no further treatment (Control Group) will undergo the following procedures and assessments:
at each visit (every 12 weeks.)
 1. physical examination
 2. vital signs
 3. ECOG performance status
 4. Weight
 5. pregnancy test (serum or urine) for female patients of child-bearing potential
 6. Clinical chemistry and haematology (CBC + differential platelet count; creatinine; total bilirubin; AST; ALT; alkaline phosphatase; LDH; albumin; glucose; potassium; sodium; calcium)
 7. documentation of AEs/SAEs
 8. documentation of concomitant medications and procedures
 9. CEA and CA 19-9 analysis
 10. CT/MRI/PET scan as per baseline assessment

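### The visit schedule gives untreated controls a 12-weekly pregnancy test but sets no timed test after baseline for women on regorafenib plus durvalumab

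*Combined protocol and SAP*

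**What the plan says.** The introduction to Section 8 says that the timing of assessments is set in 8.1 and that their content is described in 8.2. It adds that procedures not indicated count as the site's standard care and are outside the study.

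At screening, both arms are tested. Table 1 has a row for "Hematology, chemistry, coagulation and pregnancy test" with the window "28 to 1 day before randomization", and 8.1.1 asks for a "pregnancy test (serum or urine) for female patients of child-bearing potential". The same words return in 8.1.2 as item 5 of the control-group list, which applies at each 12-weekly visit.

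The other list in 8.1.2 begins "Patients allocated to Treatment arms will undergo the following procedures and assessments" and has nine items. None is a pregnancy test. Table 2 has no pregnancy row, and its baseline column, "From -7 days to Day 1 Cycle 1", repeats haematology, coagulation and chemistry only. The end-of-treatment list (8.1.3) and the follow-up list (8.1.4) have none either.

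Footnote d to Tables 1 to 3 includes this entry: "Pregnancy test (a positive urine test will be confirmed with a serum pregnancy test) during the study (for woman of childbearing potential". It gives no visit, interval or arm. It then sets the rule that depends on detection: "If a patient becomes pregnant while in the study, the study treatment must be immediately discontinued".

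On relapse, 8.1.2 states: "Patients in the control arm will be offered to crossover to regorafenib plus durvalumab".

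**The concern.** Followed as written, 8.1.2 looks for pregnancy at fixed points in women who are not taking the study drugs and at no fixed point after baseline in women who are. No reason is given for the difference.

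The protocol treats exposure in pregnancy as serious: pregnant women are excluded, contraception is required until 90 days after the last durvalumab dose, and treatment must stop as soon as a patient is pregnant. The stop rule can act only on a pregnancy that is known. If contraception fails, detection in the treated arm depends on an untimed footnote test, on local practice or on the woman's own report. Controls who cross over start the same drugs, and no timed test on treatment is stated for them either.

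**Working it through.** The plan states no figure for this point. The check sets the passages side by side and then works out the intervals they imply.

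**Where a post-baseline pregnancy test is timed**

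| Place | Regorafenib plus durvalumab | Control |
|---|---|---|
| 8.1.2 list | none in nine items | item 5, every 12 weeks |
| Schedule table | Table 2: no row | Table 3: no row |
| 8.1.3 End of treatment | none | none |
| 8.1.4 Follow-up | none | none |
| Footnote d | during the study, no time | during the study, no time |
| 8.2.1.3 | enrolment procedure; acts on a positive result before treatment | same |
| Section 9, laboratory tests | pregnancy tests mentioned, no time | same |
| 9.8 | self-report and stopping, no schedule | self-report, no schedule |

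For controls, the text of 8.1.2 and Table 3 disagree. For the treated arm, every place agrees in giving no time.

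**Interval in the treated arm**

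Inputs: 28-day cycles with regorafenib on Days 1 to 21, up to 12 cycles (Synopsis, 7.1, 7.3.1); screening 1 to 28 days before randomization (Table 1). Assumptions: Day 1 falls on the randomization date and there is no dose delay.

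- Day 1 of Cycle 1 to Day 21 of Cycle 12: 11 × 28 + 20 = 328 days.
- From the screening test: 328 + 1 = 329 to 328 + 28 = 356 days, or 47.0 to 50.9 weeks.
- Footnote d waives a repeat for procedures done within 72 hours before Day 1. If that line is read as requiring a repeat of an older pregnancy test, the interval is 328 + 0 = 328 to 328 + 3 = 331 days.

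**Interval in the control arm, counted the same way**

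- Screening to the first 12-weekly test: 84 + 1 = 85 to 84 + 28 = 112 days.
- Between later tests: nominally 84 days.
- With the ±7-day visit window in 8.1.2, the first interval can reach 112 + 7 = 119 days and a later one 84 + 14 = 98 days.

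**Number of timed tests over 12 cycles (12 × 28 = 336 days, 48 weeks)**

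- Treated arm: 0 after baseline.
- Control arm under 8.1.2: at most 4 (weeks 12, 24, 36 and 48).

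**How many patients the full interval describes**

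Cycle 12 starts 11 × 28 = 308 days, or 10.12 months, after Day 1. With the plan's 10-month median in the experimental arm, an exponential curve, and relapse as the only reason to stop, 2^(−10.12/10) = 0.50 of patients start Cycle 12. About half would therefore be exposed for the whole interval, and fewer if toxicity also stops treatment. Dose delays, which Section 8 allows, would lengthen it.

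**The case against.** The strongest reply is that testing on treatment is already in the plan. Footnote d is marked on Table 2's laboratory rows and lists a pregnancy test during the study. Section 9 counts pregnancy tests among the laboratory safety tests, in a section about evaluating patients before, during and after treatment. This stands as evidence of intent. A reader might infer from 8.1.2 that treated women are never tested, or that the sponsor chose to test only untreated women. The documents support neither. Table 3 lacks the row that the 8.1.2 control list calls for, which suggests a drafting slip, possibly an item placed in the wrong list.

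Intent does not supply a time, however. Table 1 names the pregnancy test in its row label and Table 2 does not, so reading footnote d as a test at every marked visit would be an inference. Section 8 sends the reader to 8.1 for timing, and 8.1 gives none for this arm.

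It can also be said that the safeguards are adequate: a screening test, contraception, a duty to report at once, immediate stopping, and visits at least monthly on treatment. They do lower the risk and limit the weight of the point. They do not replace a test that would find a failure of contraception before the woman suspects it.

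**Conclusion.** The point holds as an inconsistency in the safety schedule that should be corrected. After baseline, no place in the document times a pregnancy test for women on regorafenib plus durvalumab. For a 12-cycle completer without dose delay the gap is 329 to 356 days (328 to 331 days on the repeat reading of the 72-hour line), against 85 to 112 days to the first control test and nominally 84 days after that.

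These are intervals between timed tests. They should not be read as durations of undetected exposure, since women attend often and must report a pregnancy at once. The document does not say how many women of child-bearing potential will enrol, so no total number affected can be given. The DFS analysis, sample size and error rates are untouched.

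**What to change.** Add a pregnancy test for women of child-bearing potential to the treatment-arm list in 8.1.2 and as a row in Table 2, at existing visits and at least every 12 weeks. Day 1 of each cycle is one option; the documents support having a time but do not dictate that frequency. State that the same test applies to controls who cross over, and add the row to Table 3 so that it matches the 8.1.2 control list. Footnote d can then refer to those rows.

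The cost is a change of wording and a urine test at visits already planned: up to 4 tests per woman over 48 weeks if done every 12 weeks, or at most 12 if done on Day 1 of each cycle. No extra visit is needed.

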8.1.3 End of treatment

End of treatment is defined as the last planned dosing visit within the 12-month dosing period. For patients who discontinue durvalumab prior to 12 months, end of treatment is considered the last visit where the decision is made to discontinue treatment. All required procedures may be completed within \pm 7 days of the end of

treatment visit. Repeat disease assessment is not required if performed within 28 days prior to the end of treatment visit.

Assessments for patients who have completed the treatment and achieved disease control, or have discontinued durvalumab due to toxicity in the absence of confirmed progressive disease:

1. Prior/concomitant medications
2. Complete physical examination
3. Vital signs
4. ECOG performance status
5. 12 - lead ECG
6. Tumor imaging/response assessment
7. Clinical chemistry and haematology (CBC + differential platelet count; creatinine; total bilirubin; AST; ALT; alkaline phosphatase; LDH; albumin; glucose; potassium; sodium; calcium)
8. Documentation of AEs/SAEs

8.1.4 Follow-up

During the early follow-up phase (Month 13-Month 24, Table 2 and 3) all patients will undergo the following visits every 3 months.

During the late follow-up phase (Month 25 to Month 60) all patients will undergo the following visits every 4-6 months.

1. Safety assessments
2. Physical examination
3. Vital signs
4. Eastern Cooperative Oncology Group [ECOG] performance status
5. CT/MRI/PET scan as per Investigator's choice
6. CEA and CA 19-9 analysis
7. Clinical chemistry and haematology (CBC + differential platelet count; creatinine; total bilirubin; AST; ALT; alkaline phosphatase; LDH; albumin; glucose; potassium; sodium; calcium; amylase; lipase)
8. Concomitant medications
9. For patients with documented relapse: visit (according to SoC) or telephone contact to document OS.

8.2 Study Procedures

All study related investigations are to be performed by the Investigator or medically qualified study personnel delegated by the Investigator. The Investigator is considered responsible for the overall treatment of the patient.

All procedures will be carried out at the times indicated in Table 1, [Table 2](#), and [Table 3](#) and in Section 8.1.

8.2.1 Enrolment Procedures

8.2.1.1 Informed consent

Before inclusion into the study, each patient will be informed, both verbally and in writing, about the nature of the study, the anticipated risks and discomfort associated with the study and also about the right to discontinue participation in the study at any time.

Prior to participation in the study, each patient will have signed the written ICF which has been approved by the Independent Ethics Committee (IEC).

No study activities may take place until the informed consent documents have been signed.

8.2.1.2 Demographics and medical history

All relevant hospital records are to be made available to the Investigator prior to randomization. Medical history includes details of: any neoadjuvant or adjuvant chemotherapy; surgical or other procedure; tissue samples and documentation relating to tumour assessment; and prior antitumoral drugs.

8.2.1.3 Pregnancy test

A serum or urine pregnancy test will be administered to all female patients of childbearing potential, defined as follows:

- Premenopausal women capable of becoming pregnant, including women on oral, injectable or mechanical contraception.

If the result of the pregnancy test is positive, the patient will be withdrawn from the study prior to administration of study treatment.

Female patients who become pregnant during the study or within 6 months after receiving the last administration of study treatment will be followed through birth or termination of the pregnancy. The Investigator or designee must report all pregnancies to the Study Contact for Reporting Serious Adverse Events (Section 9.2) immediately after becoming aware of the event.

8.2.2 Safety Assessments

8.2.2.1 Physical examination

Physical examinations will include height (at screening), weight, and a general assessment of overall body systems (cardiovascular, respiratory, gastrointestinal, etc.).

8.2.2.2 Vital signs

Assessment of vital signs includes systolic and diastolic blood pressure, heart rate, body temperature and respiratory rate. Body temperature should be measured using the same methodology at each assessment and it should be measured in decimals.

8.2.2.3 Eastern Cooperative Oncology Group performance status

The ECOG performance status is a standardised set of scales and criteria used to assess how a patient's disease is progressing, how the disease affects the daily living abilities of the patient and to determine appropriate treatment and prognosis. The assessment is provided in Appendix 1.

8.2.2.4 Electrocardiogram

Perform a 12-lead resting electrocardiogram (ECG) before the begin of the treatment, at the end-of-treatment and if clinically indicated. Patients should be in a supine position for at least 10 min before recording. ECG tracings will be reviewed by a qualified physician for assessment of QT interval as well as signs of qualitative abnormalities, including evaluation of rhythm, ST segment morphology, T wave morphology, and presence/absence of U wave.

The original ECG tracing will be maintained in the source documentation of each patient.

8.2.2.5 Clinical chemistry, coagulation and hematology

The Investigator must review the laboratory assessments (initialled and dated) within 24 hours after the receipt of results. Out of range values will be interpreted by the Investigator with a comment of "not clinically significant" (NCS) or "clinically significant" (CS). Clinically significant abnormal laboratory values must be repeated at the appropriate clinical follow-up arranged by the Investigator and documented on the lab report until the lab value has stabilised or has returned to a clinically acceptable range (regardless of relationship to study treatment). Any laboratory value that remains abnormal and is judged to be clinically significant will be followed according to accepted medical standards for 30 days or until resolution of the abnormality.

Procedure does not have to be repeated if performed within 72 hours prior to Cycle 1 Day 1 (i.e. first day of dosing).

All haematology, coagulation and blood chemistry samples will be processed at the local laboratory according to institutional procedures. Blood samples will be collected for the following analyses:

Chemistry

- albumin
- total bilirubin
- alkaline phosphatase (ALP)
- alanine aminotransferase (ALT)
- aspartate aminotransferase (AST)
- LDH
- glucose
- sodium
- potassium
- chloride
- magnesium
- urea
- calcium
- creatinine
- total protein
- amylase
- lipase

Coagulation Profile

- aPTT
- PT
- INR

Haematology profile (complete blood count [CBC])

- red blood cell (RBC) count
- white blood cell (WBC) count and differential (neutrophils, eosinophils, lymphocytes, monocytes, basophils)
- haemoglobin (Hgb)
- haematocrit (Hct)
- platelet count

A Plasma sample will be stored for potential future research for which specific experimental plan and informed consent form will be developed

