5.2.4 Toxicity

Analyses for toxicity will be based on the safety population. For each patient and for each type of toxicity, the worst grade of toxicity/adverse events observed over the whole treatment period according to CTCAE version 5 will be presented and used for the analyses. Two sets of statistical analyses will be performed to compare toxicity in the two treatment groups. In the first set the whole pattern of toxicity (all grades) will be considered for each item; analysis will be done by a linear rank test. In the second set toxicity will be defined as severe (mostly including grade 3 or higher) and not severe (mostly including grades up to 2) and analysis will be performed by chi-square or the Fisher's exact test, as appropriate.

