7.5.1 Regorafenib Dose Levels

Dose Level	Daily Dose	Daily Dose	Daily Dose
Dose level patient is currently receiving	90 mg	60 mg	30 mg
Dose level -1	60 mg	30 mg	Not permitted*
Dose level -2	30 mg	Not permitted*	Not permitted*

* If a dose reduction is required to manage a regorafenib-related AE, then regorafenib must be discontinued.

Recommended dose modification for toxicities except hand-foot-skin reaction, hypertension and ALT/AST/bilirubin			
NCI-CTCAE v5.0 ^a	Dose interruption	Dose Modification ^b	Dose for Subsequent Cycles
Grade 0-2	Treat on time	No change	
Grade 3	Delay until ≤ Grade 2 ^c	Reduce by 1 dose level	If toxicity remains < Grade 2, dose re-escalation can be considered at the discretion of the treating investigator. If dose is re-escalated and toxicity (Grade 3) recurs, institute permanent dose reduction.
Grade 4	Delay until ≤ Grade 2 ^c	Reduce by 1 dose level. Permanent discontinuation can be considered at treating investigator's discretion.	

a. NCI-CTCAE = National Cancer Institute - Common Terminology Criteria for Adverse Events, version 5.0
b. Excludes alopecia, non-refractory nausea/vomiting, lymphocyte count decreased, non-refractory hypersensitivity and nonclinical and asymptomatic laboratory abnormalities.
c. If no recovery after a 4 week delay*, treatment should be permanently discontinued unless subject is deriving clinical benefit.

If greater than 2 dose level reductions are required, regorafenib will be discontinued and the rest of the study follow up may be continued. The following tables outline dose adjustments for toxicities related to regorafenib except hand-foot skin reaction, hypertension and liver function test abnormalities.

The table above outlines dose adjustments for hematologic and non-hematologic toxicities related to regorafenib except PPES and hypertension. In addition to these recommended dose modifications, subjects who develop diarrhea, mucositis, anorexia or other events predisposing to fluid loss or inadequate fluid intake should be carefully monitored and rehydrated as clinically necessary. This is in order to minimize the risk of postural hypotension and renal failure.

Regorafenib Dose Modification Guidance, Non-Immune Toxicities: Hand-Foot Skin Reaction Related to Regorafenib Only

CTCAE v5.0 Grade	Occurrence	Recommended Management
G1	Any	
 Maintain dose level and immediately institute supportive measures for symptomatic relief.

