8.2.2.6 Adverse events (AEs)

After informed consent is obtained, AEs will be recorded continuously through the study conduct, and managed as outlined in Section 9 and according to the Safety Management Plan developed for this study. Events that occur prior to initiation of study treatment will be assessed as “not related” to study medication; AEs that occur after the first administration of study medication will be assessed as treatment-emergent AEs (TEAEs).

Adverse events will be categorised based on severity; relationship to study treatment and seriousness and according to National Cancer Institute's Common Terminology Criteria for Adverse Events (NCI CTCAE) Version 5.0.

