9.7.6 Laboratory Test abnormalities

Laboratory test results will be recorded on the laboratory results form of the eCRF.

Any laboratory result abnormality fulfilling the criteria for an SAE should be reported as such, in addition to being recorded as an AE in the eCRF.

Any treatment-emergent abnormal laboratory result which is clinically significant, i.e., meeting one or more of the following conditions, should be recorded as a single diagnosis on the AE page in the eCRF:

- Accompanied by clinical symptoms
- Leading to a change in study medication (e.g. dose modification, interruption or permanent discontinuation)
- Requiring a change in concomitant therapy (e.g. addition of, interruption of, discontinuation of, or any other change in a concomitant medication, therapy or treatment).

This applies to any protocol and non-protocol specified safety and efficacy laboratory result from tests performed after the first dose of study medication, which falls outside the laboratory reference range and meets the clinical significance criteria.

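### Non-serious laboratory AEs are ascertained unequally by arm, and Section 5.2.4 does not say that laboratory toxicity is graded from the recorded values

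*Combined protocol and SAP*

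**What the plan says.** Section 9.7.6 sends all laboratory results to the eCRF laboratory form. It then says which of them become AEs: "Any treatment-emergent abnormal laboratory result which is clinically significant, i.e., meeting one or more of the following conditions". There are three conditions, and one is enough: "Accompanied by clinical symptoms"; "Leading to a change in study medication (e.g. dose modification, interruption or permanent discontinuation"; or a required change in concomitant therapy. The rule covers results "from tests performed after the first dose of study medication". A separate sentence requires an abnormality that meets SAE criteria to be reported as an SAE and also recorded as an AE.

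Section 8.2.2.6 ties the term treatment-emergent to dosing: "AEs that occur after the first administration of study medication will be assessed as treatment-emergent AEs (TEAEs". Section 8.2.2.5 adds the investigator's comment on significance ("Out of range values will be interpreted by the Investigator with a comment of" not clinically significant or clinically significant) and sets out repeat testing and follow-up.

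Section 8.1.2 and Table 3 give controls chemistry, haematology and AE/SAE documentation every 12 weeks. In Section 7.5.1, footnote b to the general regorafenib table exempts lymphocyte decreases and "non-refractory hypersensitivity and nonclinical and asymptomatic laboratory abnormalities" from dose modification.

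Section 5.2.4 analyses "the worst grade of toxicity/adverse events observed over the whole treatment period according to CTCAE version 5" and plans two sets of tests between the two treatment groups. One is a linear rank test on all grades of each item. The other is a chi-square or Fisher test of severe against not severe. The analysis set is the safety population, which Section 5.1 limits to patients with at least one dose.

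**The concern.** CTCAE laboratory grades depend mainly on the measured value. Under Section 9.7.6, whether a non-serious value reaches the AE page depends on having had a first dose and on whether someone acted on the result. Both differ by arm, and the investigator knows the arm. If 5.2.4 takes its laboratory grades from the AE page, a between-arm difference can reflect recording practice rather than drug effect. Within the treated arm, some high-grade values could also be missed. The synopsis lists adverse events and toxicity as a secondary endpoint, and this would be the randomized evidence on laboratory safety for the combination.

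This problem is separate from the definition of the safety population. Widening that population to include untreated controls would bring them in with laboratory AEs recorded under a different rule. The comparison would then look valid without being so.

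**Working it through.** The plan states no figure on this point, so the check sets the sections side by side.

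**1. Does the 9.7.6 rule reach a control before crossover?** It needs a treatment-emergent result (defined by first administration in 8.2.2.6) from a test after the first dose. A control has no first dose before crossover, so the rule does not apply. The routes left are the SAE sentence in 9.7.6, the general AE definition in 9.1.1 (which includes abnormal laboratory findings) and AE reporting from consent in 9.2. None of these gives sites a criterion for a non-serious laboratory value in a control.

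**2. Which asymptomatic Grade 3-4 values are captured in treated patients?**
- AST/ALT: Appendix 3 starts Grade 3 above 5 x ULN with normal baseline. The liver table in 7.5.1 interrupts regorafenib above 5 x ULN with no symptom condition. The study-medication condition is met, so the value is recorded.
- Amylase/lipase: Appendix 3 holds study drug for asymptomatic levels above 2 x ULN. Again recorded.
- Values covered by footnote b, such as lymphocyte decreases: no dose modification is called for. With no symptoms and no other action, none of the three conditions is met and recording is not required.

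**3. Where does judgement enter?** Section 7.4.1 says dose modification is not required for laboratory abnormalities judged not clinically significant. Section 9.7.6 defines clinical significance partly by a change in study medication. Outside the tables with fixed actions this is circular: a value judged not significant need not prompt a change, and without a change it need not count as significant.

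**4. How often is each arm tested?** In Table 2, the haematology and chemistry panels scheduled after the first dose, up to Day 1 of cycle 12, are 3 (cycle 1) + 2 (cycle 2) + 10 (Day 1 of cycles 3 to 12) = 15. Day 1 of cycle 12 falls at 11 x 4 = 44 weeks. By then a control has had panels at weeks 12, 24 and 36, which is 3. On an undelayed schedule the common times are Day 1 of cycles 4, 7 and 10 (3, 6 and 9 cycles x 4 weeks = weeks 12, 24 and 36). A worst grade over all visits would favour detection in the treated arm even with identical recording rules. Coagulation does not appear in Table 3, so it cannot be compared.

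**5. Illustration of size.** Take 91 per arm (Section 4.2), and assume that all 91 controls are analysed and that none has a recorded event on the item. For k events against none, two-sided Fisher p = 2 x C(91,k)/C(182,k).
- k = 5: p = 0.059
- k = 6: p = 2 x 0.01435 = 0.029

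Six recorded patients on one item (6/91 = 6.6%) would therefore give nominal significance if no control events were recorded. In the planned severe/not-severe test, those six would need a severe abnormality of the same item.

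**The case against.** Several points on the other side are sound, and they limit what can be claimed.

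- A reader might infer that the CS/NCS comment in 8.2.2.5 decides what counts as toxicity. It does not. It governs review, repeat testing and follow-up, while 9.7.6 defines clinical significance for AE entry by listed conditions, two of which need no symptoms.
- A reader might infer that controls can have no laboratory AE at all. The documents do not say so. Section 9.7.6 says what should be recorded and does not forbid other entries, and the SAE route, 9.1.1 and 9.2 remain open to controls. What survives is that the specific non-serious rule does not reach controls, so their ascertainment is left to a vaguer route.
- A reader might infer that asymptomatic Grade 3-4 values are lost in general. AST/ALT and amylase/lipase are captured, as shown above. In the table as extracted, footnote b also marks only the dose-modification column and not the interruption column. A Grade 3-4 delay, if one is made, would itself trigger recording. The loss is limited to values that prompt no action.
- A reader might infer that abnormalities permitted at entry become toxicity in one arm. Section 9.2 sends pre-existing conditions found before randomization to medical history unless they worsen, so this does not follow.
- Section 5.2.4 does not name the AE page as its source, and the values are on the eCRF. Loss from the analysis is a risk left open, not a stated rule.
- The illustration assumes 91 untreated controls, whom 5.1 excludes at present, and a zero control count.

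These points narrow the concern but do not remove it. The stated recording rule still differs by arm, and the analysis section still plans a between-group test without fixing the source of laboratory grades.

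**Conclusion.** The concern holds in a limited form. Read literally, Section 9.7.6 gives unequal ascertainment of non-serious laboratory AEs between arms before crossover, in an open-label trial. It also leaves unrecorded those asymptomatic Grade 3-4 values in treated patients that lead to no action. Section 5.2.4 does not protect the comparison, because it never says that laboratory grades come from the recorded values.

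The size cannot be derived: the documents give neither background laboratory rates nor the share of values that prompt no action. The 6/91 against 0/91 result shows how few patients would matter under the stated assumptions and is not an estimate of bias. The conclusion rests on the literal wording of 9.7.6 and 8.2.2.6 and on laboratory toxicity being taken from the AE page, which the plan neither states nor excludes. The change should be made, because it is cheap and can be specified before analysis. Sample size and the primary endpoint are not affected.

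**What to change.** In Section 5.2.4:

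1. State that laboratory toxicity grades are derived by program from the eCRF laboratory values under CTCAE v5.0, with shift from baseline, in both arms and whatever the CS/NCS comment.
2. Restrict the between-arm comparison to chemistry and haematology tests scheduled in both arms (no coagulation), at the common 12-weekly visits, before crossover or any other anticancer therapy.
3. Define the set for this comparison so that it includes never-dosed controls, whom the 5.1 safety population now excludes.
4. Show the other on-treatment values for the treated arm descriptively.
5. Keep the 9.7.6 conditions for clinical AE reporting only.

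This changes no clinical rule and needs no new data collection, because 9.7.6 already sends the results to the eCRF laboratory form. The cost is SAP wording and programming. The downside is that more low-grade abnormalities will appear in the tables.
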